9.3.5. Identification of Outcomes

9.3.5.1. Primary Outcome (Effectiveness)

The primary outcome for this study is the occurrence of new HZ infection. Occurrence of new HZ infection will be identified by the first presence of a diagnosis code for HZ infection (ICD-10 code: B02, Zoster [herpes zoster]) on at least one claim during follow-up. This algorithm was based on previous studies by Yawn et al.¹⁶ and Kim et al.¹⁷ which found that the positive predictive values (PPVs) for the presence of one diagnosis code for HZ were 85.2% and 86.2%, respectively, compared to the gold standard of medical record review.

Due to the administrative claims process, patients may receive a diagnosis code for HZ infection on the date of RZV receipt. For this reason, diagnostic codes for HZ infection that occur on the date of receipt of RZV will not be used to exclude prevalent cases of HZ (Section 9.2.2) and will not be counted as outcomes (Section 9.2.5).

9.3.5.2. Secondary Outcome (Safety)

The secondary outcome for this study is disease flare: UC flare within the UC cohorts and RA flare within the RA cohorts.

For the UC cohorts, the secondary outcome will be defined by an algorithm based on the claims-based indicator of UC flare in the 90 days following the cohort entry date. Based on published literature,^{18,19} the claims-based composite algorithm of UC flare will include a combination of the following components:

- Change in UC therapy (ie, new start or switch);
 - Corticosteroids (oral, rectal, or injection);
 - 5-aminosalicylates (oral or rectal);
 - Immunosuppressants (ie, azathioprine, 6-mercaptopurine, cyclosporine, tacrolimus);
- Emergency room visit with UC as primary diagnosis;

- Hospitalization with UC as primary diagnosis;
- UC-related surgery (ie, colectomy, proctocolectomy).

For the RA cohorts, the secondary outcome will be defined by an algorithm based on the occurrence of a claims-based indicator of RA flare in the 90 days following cohort entry date. Based on published literature,^{20,21,22,23} claims-based composite algorithm of RA flare will include a combination of the following components:

- Change in RA therapy (eg, new start or switch from monotherapy to combination therapy);
 - Corticosteroids (oral or injection): initiation of, or change in, treatment with a short-acting oral glucocorticoid (eg, methylprednisolone 6-day dosing pack) or any parenteral glucocorticoid injection, excluding corticosteroids administered the same day as infusions for RA therapy;
 - Conventional synthetic disease-modifying antirheumatic drugs (csDMARDs) (ie, methotrexate, sulfasalazine, hydroxychloroquine, leflunomide);
- Emergency room visit with RA as primary diagnosis;
- Hospitalization with RA as primary diagnosis.

The claims-based indicators of disease flare will be identified based on drug (NDC and American Hospital Formulary Service [AHFS]), procedure (Healthcare Common Procedure Coding System [HCPCS], CPT[®], and International Classification of Diseases, 10th Revision, Procedure Coding System [ICD-10-PCS]), and diagnosis (ICD-10) codes. The specific codes that will be utilized to identify UC and RA disease flares are provided in [Annex 3](#).

For both UC and RA flare, a new start or switch will be defined as a dispensing of one of the medications listed above with no dispensing for the same medication in the prior 365 days. As long-term corticosteroids are widely used in the treatment of RA,²⁴ this definition will help distinguish between a new dispensing for the treatment of flare versus long-term therapy. Additionally, days' supply of oral corticosteroids will be taken into account to identify short-acting treatments (eg, limiting to dispensing with a days' supply of 7 days or less).

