As patients that have UC and RA may have different clinical characteristics compared to patients that have only one of the two diseases, the number of patients that have both diagnoses will be quantified. Additionally, a sensitivity analysis will be conducted in which the association between RZV exposure and the primary and secondary outcomes is assessed after excluding patients with both UC and RA from the exposure cohorts.

To assess the effect of prior Zostavax vaccination on subsequent RZV effect, an analysis will be performed where the study population is restricted to patients with at least 5 years of enrollment prior to cohort entry. Within this subset, the analysis will be conducted separately among patients with and without Zostavax vaccination during this baseline 5-year period. The effect of prior Zostavax exposure will be informed by the extent to which the estimate of RZV effect differs according to strata of prior Zostavax exposure.

It is possible that the comparator cohorts could include patients previously vaccinated with RZV more than 365 days earlier. To address this potential exposure misclassification, a sensitivity analysis will be performed, for which the study population will be restricted to patients with enrollment that extends back to 20 October 2017 and who do not have any prior administration of RZV during that time. Finally, a sensitivity analysis will be conducted for HZ in which patients are stratified based on their amount of available follow-up time.

Misclassification of disease flares is possible when using claims-based algorithms (for example, patients may change therapy for reasons other than disease flares), leading to over- or under-estimation of the outcome; thus, alternative definitions will be explored and outlined in the SAP as sensitivity analyses. Specifically, sensitivity analysis will explore using a more conservative definition based on only UC-related surgeries or ER and hospitalizations with UC or RA as the primary diagnosis, as well as evaluating more expansive definitions inclusive of other medications of interest, such as biologics or other JAK inhibitor treatments.

Additional sensitivity analysis may be performed if needed.

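### The steroid component of the flare outcome is not tied to UC or RA, so steroids given for other reasons can count as flares and bias the safety hazard ratio

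*Protocol*

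**What the plan says.** Section 9.3.5.2 builds a composite flare outcome over 90 days for each disease. The healthcare-contact components name the disease: for UC, "Emergency room visit with UC as primary diagnosis" (admissions likewise); for RA, "Hospitalization with RA as primary diagnosis" (emergency visits likewise).

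The drug components do not. The UC list has "Corticosteroids (oral, rectal, or injection" by any of those three routes. The RA list has "initiation of, or change in, treatment with a short-acting oral glucocorticoid (eg, methylprednisolone 6-day dosing pack) or any parenteral glucocorticoid injection", followed by one carve-out: "excluding corticosteroids administered the same day as infusions for RA therapy". The UC list has no such carve-out.

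Three further provisions bear on this:

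- Section 9.3.5.2 defines a new start as no dispensing of the same drug in the previous 365 days. It also uses days' supply to pick out short oral courses, with 7 days or less as the example.
- Annex 3 identifies steroids by HCPCS and AHFS codes with no paired diagnosis. The route restriction is footnoted on the AHFS rows only. J7312, the intravitreal dexamethasone implant, is in both the UC and the RA list.
- Section 9.7.4 concedes that "patients may change therapy for reasons other than disease flares". It names two alternatives: a "more conservative definition based on only UC-related surgeries or ER and hospitalizations with UC or RA as the primary diagnosis", and wider definitions that add biologics or other JAK inhibitors.

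**The concern.** Two kinds of component sit in one composite under different standards of evidence. An emergency visit counts only if it was for the disease. A steroid claim counts if it is new and, for oral courses, short. A 6-day pack for a respiratory infection, or a triamcinolone shoulder injection in a UC patient, can pass those tests.

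Flare after vaccination is a named secondary safety objective (Section 8) in a study designated a PASS and an FDA post-marketing commitment (Section 7). Events that are not flares add noise to the hazard ratio, and in the simplest case they shrink a real increase toward no difference. The protocol gives positive predictive values for the herpes zoster code (85.2% and 86.2%, Section 9.3.5.1) but none for the flare algorithm, so the reader cannot judge how many counted flares are real.

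**Working it through.** The protocol states no flare rate, flare power or flare predictive value, so there is no figure of its own to reproduce. The Section 9.5 precision figures concern herpes zoster only. Every risk below is an assumption, shown over a range.

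**1. Do the existing limits address the reason for treatment?**

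| Limit | Cohorts | What it separates |
|---|---|---|
| No dispensing of the same drug in prior 365 days | UC and RA | new from continuing use |
| Short days' supply, oral steroids | UC and RA | short courses from long-term use |
| Same-day infusion exclusion | RA only | infusion-day steroids from others |
| Route restriction | AHFS rows only | routes of administration |

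Only the infusion exclusion concerns why the steroid was given.

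**2. Non-flare events equally common in both cohorts.** Assume true 90-day flare risks of 8% (comparator) and 12% (vaccinated), a ratio of 1.5. Add a non-flare steroid risk f to each, ignoring overlap. Observed ratio = (0.12 + f)/(0.08 + f).

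| f | Observed ratio | Share of the 0.5 excess lost |
|---|---|---|
| 1% | 0.13/0.09 = 1.44 | 11% |
| 2% | 0.14/0.10 = 1.40 | 20% |
| 4% | 0.16/0.12 = 1.33 | 33% |
| 8% | 0.20/0.16 = 1.25 | 50% |
| 12% | 0.24/0.20 = 1.20 | 60% |

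**3. The same on the hazard scale.** Let r be the true comparator flare risk, p the non-flare steroid risk, h0 = −ln(1 − r), hf = −ln(1 − p), and m the ratio of non-flare hazards, vaccinated to comparator. Then observed HR = (HR × h0 + m × hf)/(h0 + hf).

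With m = 1, r from 2% to 10% and p from 1% to 10%:

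- true 1.25 is seen as 1.04 to 1.23;
- true 1.5 is seen as 1.08 to 1.46;
- true 2.0 is seen as 1.16 to 1.91.

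Worked case: r = p = 5%, so h0 = hf, and true 1.5 becomes (1.5 + 1)/2 = 1.25.

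**4. Non-flare events not equally common.** Section 9.2.5.2 counts flares from the cohort entry date. For vaccinated patients that is the day of an RZV claim. For comparators it is a randomly drawn day in a 4-week window (Section 9.2.3.2.2.2), with no contact required. So m need not equal 1. With r from 2% to 10% and p from 3% to 10%:

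| m | True HR 1.0 seen as | True HR 1.5 seen as |
|---|---|---|
| 0.8 | 0.83 to 0.96 | 0.91 to 1.34 |
| 1.25 | 1.06 to 1.21 | 1.29 to 1.44 |
| 2.0 | 1.22 to 1.84 | 1.61 to 1.92 |

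At m = 1.5, a true HR of 1.5 is recovered exactly. The sign of the bias therefore depends on m, which the documents do not give.

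**5. The named alternatives.** The conservative definition removes every steroid false positive, and with it every flare treated only with drugs. The wider definitions keep all current events and add more, so they cannot remove a false positive. Neither keeps drug-treated flares while linking them to the disease.

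**The case against.** The strongest reply has five parts.

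- **The algorithm follows published work.** Section 9.9 discloses the misclassification and notes that a similar treatment-based algorithm has been used for flares after RZV. That supports keeping it as the main definition. It does not show how specific it is in this population.
- **The conservative definition already removes the problem.** For steroid false positives this is correct, and missed flares that are equally likely in both cohorts need not bias the ratio. What remains is that it answers a narrower question, about flares leading to surgery, an emergency visit or admission, with fewer events. How many fewer is not stated.
- **The 365-day rule weakens the UC premedication example.** This stands in part. Repeated premedication with the same steroid would not be a new start; mainly the first would qualify. Starting an infused biologic may itself mark a flare, as the wider definitions in Section 9.7.4 allow.
- **A steroid claim alone may not be enough.** The algorithm "will include a combination of the following components", and how they combine is not fixed. However, the RA text refers to the occurrence of a single indicator, and Section 9.7.4 contrasts the main definition with one lacking drugs. Both suggest that a therapy change alone can qualify. If it cannot, the bias is smaller.
- **The SAP may hold more.** Section 9.7.4 sends the detail of alternative definitions there and allows further analyses. The point is therefore limited to the definitions named in the protocol.

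A reader might infer that the rule drives the safety hazard ratio toward no effect. The documents do not support that without the condition of equal false-positive rates, which the different entry dates put in doubt. A reader might also infer that steroids count whatever they were given for. The RA infusion exclusion contradicts that as a general statement.

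**Conclusion.** The concern holds in a limited form. As defined in the protocol, steroid claims need no link to UC or RA, the one reason-based exclusion covers RA only, and both code lists contain an eye implant that cannot mark either flare.

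If non-flare steroid claims are equally common in both cohorts, a true ratio of 1.5 is seen as 1.44 to 1.20 for non-flare risks of 1% to 12%, given assumed flare risks of 8% and 12%. If they are not, the bias can go in either direction. These sizes rest on assumed risks and on a lone steroid claim being sufficient. They show that the problem can matter, not that a reassuring bias has been demonstrated.

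Nor do the documents show that the literature-based main definition must be replaced. Linking steroids to a diagnosis trades sensitivity for specificity, which is a reason to report both definitions.

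**What to change.** 1. In Section 9.3.5.2, apply the same-day infusion exclusion to UC as well as RA.
2. In Annex 3, remove J7312 from both lists, and any other code that cannot mark a UC or RA flare.
3. Prespecify an added definition that keeps the drug component but counts a steroid claim only with a diagnosis: K51* for UC, or M05*/M06* except M06.1 and M06.4 for RA. For an injection the code must be on the same claim; for a dispensing, on a claim near it, with the window chosen and justified in advance. Report it beside the current definition.

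The cost is wording, an edited code list and a join on claims already to be extracted. The added definition will miss true flares that have no coded visit nearby. Because vaccination may itself coincide with a visit, the required nearby diagnosis could be found more readily in vaccinated patients, which should be considered when the window is set.

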9.3.6. Covariates

Members of the study cohorts will be described according to claims-based covariates. Unless otherwise specified, diagnoses will be identified through the presence of ICD-10 codes, while prescription medications will be identified through pharmacy dispensings or administrations. No over-the-counter medications will be assessed. Drug use and disease status will be

² CPT copyright 2022 American Medical Association. All rights reserved.

categorized as yes (code present) or no (no code present). Demographic attributes will be determined on the cohort entry date while other factors will be assessed during the 365-day baseline period, unless otherwise specified. In addition to the covariates listed below, the 50 most common diagnoses, procedures, and medications will be described during the baseline period.

9.3.6.1. Demographic Characteristics

- Age;
- Sex;
- Race/Ethnicity;
- Geographic location;
- Data source (ORD or MA-PD).

9.3.6.2. Healthcare Utilization

- Number of outpatient visits;
- Number of emergency department visits;
- Number of 3-digit diagnosis codes;
- Number of drugs dispensed;
- Hospitalizations;
 - Number of hospitalizations;
 - Number of inpatient days (among patients who have been hospitalized).

9.3.6.3. Comorbid Conditions

- Human immunodeficiency virus (HIV) infection;
- Malignancy, excluding non-melanoma skin cancer;
- Diabetes mellitus (type 1 and type 2);
- Other autoimmune diseases (eg, psoriatic arthritis, ankylosing spondylitis, systemic lupus erythematosus, Crohn's disease, Graves' disease, multiple sclerosis);
- Cardiovascular disease;
- Serious infections

9.3.6.4. Treatment History

- Tofacitinib treatment;
 - Tofacitinib dose;
 - Average daily dose in prior 91 days;
 - Cumulative dose in prior 365 days;
 - Treatment duration;
- Zostavax[®] vaccination;
- TNF inhibitor treatment (eg, etanercept, adalimumab, golimumab, infliximab, certolizumab);
- Non-TNF biologics (eg, abatacept, rituximab, tocilizumab, sarilumab, anakinra, ustekinumab, vedolizumab);
- csDMARD treatment (eg, methotrexate, sulfasalazine, hydroxychloroquine, leflunomide, azathioprine);
- Immunosuppressants (eg, azathioprine, 6-mercaptopurine, cyclosporine);
- JAK inhibitor treatment (eg, baricitinib, upadacitinib);
- Corticosteroid treatment;
 - Average daily dose (eg, None, ≤ 5 mg/day, >5 to ≤ 10 mg/day, >10 to ≤ 20 mg/day, and >20 mg/day of prednisone average dose equivalent);
 - During 30 days prior to cohort entry;
 - During 365 days prior to cohort entry;
- Number of treatments for UC/RA prior to cohort entry;
- Chemotherapy;
- Radiotherapy;
- 5-aminosalicylates (eg, mesalamine, balsalazide, olsalazine);
- Ozanimod.

Additional therapies that are approved for the treatment of UC or RA may be incorporated if they become available. All of the above covariates may be considered for inclusion in the propensity score model used for IPTW.

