9.2.2. Exclusion Criteria

Patients meeting any of the following criteria will not be included in the study:

1. Receipt of RZV (comparator cohorts only in the RZV 2-Dose analysis) during the 365 days prior to cohort entry, excluding the cohort entry date;
2. Diagnosis of HZ infection in the 365 days prior to cohort entry, excluding the cohort entry date;
 - Presence of a diagnosis code for HZ infection on the same date as RZV receipt (Dose 1 or Dose 2) will not be cause for exclusion from the study due to the administrative claims process;
3. Receipt of a solid organ transplant or hematopoietic stem cell transplant during the 365 days prior to cohort entry, excluding the cohort entry date;

4. In addition, patients with any of the following claims-based indicators of disease flare during the 91 days prior to cohort entry (as described in Section 9.2.3.2.1 for the RZV 2-Dose analysis, and in Section 9.2.3.2.2 for RZV ≥ 1 Dose analysis) will not be included in the study:
- Emergency room visit or hospitalization with UC as primary diagnosis (UC cohorts);
 - UC-related surgery (ie, colectomy, proctocolectomy) (UC cohorts); and
 - Emergency room visit or hospitalization with RA as primary diagnosis (RA cohorts).

[figure not shown]
In addition, patients meeting any of the following criteria will not be included in the RZV 2- Dose analysis:

5. Diagnosis of HZ infection within 28 days after but not including the cohort entry date (ie, Days [1,28]), as the follow up time will be assessed from day 29 after cohort entry date (Section 9.2.5.1); and
6. Occurrence of any censoring event (ie, disenrollment from health plan, death, end of the study period, or receipt of RZV) within 28 days after cohort entry date (Section 9.2.5.1).

Figure 2 summarizes the schematic for assessing patient eligibility, as well as assessment of covariates and outcomes, for (a) the RZV 2-Dose analysis and (b) the RZV ≥ 1 Dose analysis, with details outlined in the subsequent sections.

Figure 2. Schematic for Assessing Eligibility, Covariates, and Outcomes of RZV Initiators and Comparators in (a) RZV 2-Dose Analysis and (b) RZV ≥ 1 Dose Analysis

(a)

- a. Up to 32 day gaps in medical or pharmacy enrollment allowed
- b. Receipt of RZV exclusion applied to Comparator cohorts only
- c. Baseline conditions included: healthcare utilization, comorbid conditions, and treatment history

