9.7. Data Analysis

9.7.1. Propensity Score Modeling

Propensity scores that discriminate between receipt and non-receipt of RZV will be created from a wide variety of baseline demographic, comorbidity, disease severity (based on proxies for disease severity, such as treatment with advanced therapy), and comedication indicators. The propensity scores will be used to calculate IPTW to adjust for potential confounding in the comparative analysis.

There will be 4 propensity score models that, separately, will estimate propensity scores that discriminate between (1) receipt of two doses of RZV and non-receipt of RZV in UC cohorts, (2) receipt of two doses of RZV and non-receipt of RZV in RA cohorts, (3) receipt of at least one dose of RZV and non-receipt of RZV in UC cohorts, and (4) receipt of at least one dose of RZV and non-receipt of RZV in RA cohorts. If there are confounders identified that would only be appropriate to include in one model and not the other, separate propensity score models for the outcomes HZ and disease flare will be considered.

Propensity score modeling will be performed to determine and analyze the predictors of RZV receipt, incorporating dozens of predictors of vaccination status (such as age, sex, comorbidities, and concomitant medications). Propensity scores will be estimated using logistic regression that includes predictors of vaccination, including pre-specified covariates (ie, covariates included in [Section 9.3.6.1 – 9.3.6.4](#)) and empirically identified covariates based on the most frequently occurring diagnoses, procedures, and medications dispensed, as independent variables in the model and receipt of 2 doses of RZV/non-receipt (or receipt of at least 1 dose of RZV/non-receipt) as the dependent variable. Only covariates assessed during the 365-day baseline period and known (or highly suspected) to be confounders will be included in the propensity score model. The list of empirically identified covariates will be reviewed, and those covariates that are known risk factors of HZ or UC/RA disease flares will be identified and considered for inclusion in the propensity score model. Those covariates that are correlates of RZV receipt but are not risk factors for the outcomes (and therefore not confounders) will be removed from consideration. Some pre-specified

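### The pre-specified propensity covariates include no measure of baseline flare, so the flare hazard ratio of the safety objectives may keep residual confounding

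*Protocol*

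**What the plan says.** Flare within 90 days of cohort entry is the outcome of both safety objectives (Protocol Sections 8 and 9.3.5.2). It is a composite of new drug starts or switches, ER visits and hospitalizations with UC or RA as primary diagnosis, and UC surgery.

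Baseline flare enters the plan at these places:

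- **Exclusion (Section 9.2.2, criterion 4).** It drops "patients with any of the following claims-based indicators of disease flare during the 91 days prior to cohort entry". The indicators listed are ER visits and hospitalizations with UC or RA as primary diagnosis, and UC surgery. Drug-treated flares are not among them.
- **Propensity model (Section 9.7.1).** The model uses "pre-specified covariates (ie, covariates included in" Sections 9.3.6.1 to 9.3.6.4, plus empirically found covariates.
- **Utilization (Section 9.3.6.2).** "Number of emergency department visits" and hospitalizations, with no restriction to UC or RA.
- **Drug use (Section 9.3.6).** It is "categorized as yes (code present) or no (no code present", by default over the 365-day baseline.
- **Steroids (Section 9.3.6.4).** "Average daily dose (eg, None, ≤ 5 mg/day, >5 to ≤ 10 mg/day, >10 to ≤ 20 mg/day" and one higher class, in two windows: "During 30 days prior to cohort entry" and "During 365 days prior to cohort entry".
- **Number of UC/RA treatments (Section 9.3.6.4).** Amendment 2 added this to capture severity better.

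No item in Sections 9.3.6.1 to 9.3.6.4 is a prior flare, a flare count, or acute care specific to UC or RA.

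**The concern.** A patient's recent flare history is an obvious candidate confounder here. It plausibly influences whether and when a vaccine is given, and it plausibly relates to whether another flare is recorded in the next 90 days. Exclusion 4 shows that the protocol already regards recent flare as relevant, but it covers only the severe forms in the last quarter of the year. Two kinds of baseline flare therefore enter the safety comparison without a covariate of their own: severe flares on days -365 to -92, and drug-treated flares at any time in the baseline year.

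If the proxies leave the groups unequal on these, the weighted hazard ratio for flare is shifted. Should quieter patients be vaccinated more often, and prior flare raise the recorded risk, a real increase in flare could be partly hidden. Should flare-prone patients be vaccinated more often, a false signal could appear.

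**Working it through.** The protocol gives no flare rate, prior-flare prevalence or flare effect size (Section 9.5 sizes herpes zoster only), so there is no stated figure to reproduce. Two checks are possible.

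**1. How much the steroid proxy can see.** Inputs: the example classes and the two windows of Section 9.3.6.4, and the example of a short course as 7 days' supply or less in Section 9.3.5.2. The daily doses below are arithmetic examples only.

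Total needed to leave the ≤5 mg/day class = 5 × window length:
- 365 days: 5 × 365 = 1,825 mg, or 1,825 / 7 = 261 mg/day for 7 days.
- 30 days: 5 × 30 = 150 mg, or 150 / 7 = 21.4 mg/day for 7 days.

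| 7-day course | Total | 30-day average | 365-day average |
|---|---|---|---|
| 10 mg/day | 70 mg | 2.33 | 0.19 |
| 20 mg/day | 140 mg | 4.67 | 0.38 |
| 40 mg/day | 280 mg | 9.33 | 0.77 |
| 60 mg/day | 420 mg | 14.0 | 1.15 |

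- Over 365 days all four stay in the lowest non-zero class. Six courses at 40 mg/day total 1,680 mg, or 1,680 / 365 = 4.60 mg/day, the same class as one. The number of flares is hardly registered.
- Over 30 days, a recent course at 40 or 60 mg/day moves up a class. One at 10 or 20 mg/day stays with continuous low-dose use.
- Read together, the windows separate an earlier burst (30-day None, 365-day ≤5) from continuing low-dose use (≤5 in both).

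The steroid proxy is therefore coarse but informative. Yes/no drug use does not separate a long-term user of a csDMARD or 5-aminosalicylate from a new start, which is the distinction the outcome relies on. All-cause counts mix flare-related and other visits.

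**2. What an imbalance would do.** The usual external-adjustment factor is

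B = [p1(RR − 1) + 1] / [p0(RR − 1) + 1],

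where p1 and p0 are the prevalences of prior flare in vaccinated and comparator patients, and RR is the ratio of flare risk with and without prior flare. All three are assumptions: p0 = 0.30, p1 = 0.15 to 0.25, RR = 1.5 to 3. If the proxies remove a share x of the imbalance, p1 becomes q = p0 − (p0 − p1)(1 − x).

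- Mildest (RR 1.5, p1 0.25): x = 0 gives 1.125 / 1.15 = 0.978; x = 0.5 (q = 0.275) gives 1.1375 / 1.15 = 0.989; x = 0.8 (q = 0.29) gives 1.145 / 1.15 = 0.996.
- Strongest (RR 3, p1 0.15): x = 0 gives 1.30 / 1.60 = 0.812; x = 0.5 (q = 0.225) gives 1.45 / 1.60 = 0.906; x = 0.8 (q = 0.27) gives 1.54 / 1.60 = 0.963.
- Direction reversed (RR 2, p1 0.30, p0 0.20): x = 0 gives 1.30 / 1.20 = 1.083.

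With a true ratio of 1, the estimate would lie at 0.81 to 0.98 with no help from the proxies, 0.91 to 0.99 if they remove half the imbalance, and 0.96 to 0.996 if they remove 80%. It would lie above 1 if prior flare were commoner among the vaccinated.

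**The case against.** The strongest case on the other side has four parts.

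- **The specification is still open.** Section 9.7.1 screens empirical covariates for known flare risk factors, will consider a separate flare model, and leaves model selection to the SAP, which is not at hand. Section 9.2.4 allows other windows, and the steroid classes are examples. Section 9.7.3.2 lets confounders enter the weighted Cox model. This stands as flexibility, but none of it defines the variable. The empirical candidates come from the most frequent single diagnoses, procedures and medications, and the balance trigger of 0.1 acts only on something that has been measured.
- **Residual severity confounding is acknowledged.** Section 9.7.4 plans a quantitative bias analysis that names UC/RA severity and covers the secondary outcomes. That suits what cannot be measured. Prior flare components can be measured from claims, so bounding them is second best.
- **The proxies carry real information.** A reader might infer that they cannot stand in for flare history at all. The documents do not support that: the two steroid windows separate many cases, and the drug covariates cover the classes in the flare algorithm.
- **The direction is uncertain.** Section 9.3.5.2 requires no dispensing of the same drug in the prior 365 days for a new start. A drug-treated flare in the baseline year therefore generally stops that drug from counting as an outcome, which could weaken or reverse the link between prior and recorded flare. This stands for the drug components; the rule does not apply to ER visits, hospitalizations and surgery.

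**Conclusion.** The gap is real and worth closing: the stated covariate list has no baseline-flare measure, and its proxies cover earlier severe flares and drug-treated flares only in part. The flare hazard ratio may therefore keep residual confounding.

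A reader might go further and infer that the hazard ratio is confounded, or that it will hide a vaccine effect. The documents do not show that. They give neither the imbalance in prior flare nor its effect on the recorded outcome, and the washout leaves the sign open. The ranges in the working rest wholly on assumed prevalences, risk ratios and shares removed, and show only that a shift from under 1% to about 9% is conceivable if the proxies do at least half the work. The point concerns the safety objectives and leaves the herpes zoster objectives untouched.

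**What to change.** Add to Section 9.3.6, and include in the two ≥1 Dose propensity models or in the separate flare model that Section 9.7.1 allows:

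- **(a)** ER visits or hospitalizations with UC or RA as primary diagnosis, or UC surgery, on days -365 to -92, as 0, 1 or ≥2. Days -91 to -1 are zero for everyone by exclusion 4.
- **(b)** The number of short oral steroid courses (days' supply 7 or less) and steroid injections in the baseline year, counted without the 365-day new-start rule. Applying that rule back to day -365 would need data to about day -730, while Section 9.2.1 requires only 365 days of enrollment.
- **(c)** A new start of another drug from the Section 9.3.5.2 list late in the baseline year, with no earlier fill of it in that year; for example a first fill on days -180 to -1. Its look-back is shorter than the outcome's, which is acceptable for a covariate.

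End all three before the entry date, because flare follow-up starts on that date (Section 9.2.5.2). Report standardized differences before and after weighting.

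The cost is a protocol or SAP sentence, a few lines of code using lists already in Annex 3, and about 4 to 6 parameters per model. Levels may need collapsing in the UC cohort, which is probably the smaller: Table 1 counts 202,619 UC and 446,618 RA patients before restriction to tofacitinib users and does not split those users by disease.
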